5. SAMPLE SIZE AND POWER

The planned sample size of approximately 240 subjects (120 per group) is based on assumed responder percentages for placebo and NAL ER of 25% and 45%, respectively. These responder percentages represent estimates based on the Week 10 data from the TR03 study. Power is set at 90% with a 2-sided significance level of 0.05.

5.1 Responder percentage assumptions

In the TR03 study, all those who achieved a 50% reduction in WI-NRS itch also achieved at least a 4-point reduction in itch from baseline, matching the responder definition for the current study. Results showed a response rate of 6 of 18 (33.3%) for the NAL ER 162 mg treatment group versus 4 of 22 (18.2%) for placebo. Of note, the placebo response in TR03 falls on the lower end of the expected range for endpoints that reflect PRO endpoints in neurologically-mediated diseases such as pain or psychiatric disease. Studies in these areas frequently show placebo responses in the 20% to 30% range and sometimes as high as 40%. The role of placebo response in dermatology has been increasingly documented and recognized in recent years. Given the small size of the TR03 dataset, and the variability of placebo response in comparable disease states, the estimate of placebo response for TR11 was set at 25%.

The NAL ER 162 mg responder rate is estimated at 45% for TR11, versus the 33.3% observed in TR03 for the following reasons: First, the TR03 endpoint was set at Week 10, and it is expected that the additional 4 weeks of active therapy will likely increase the response rate in this treatment arm. Second, experience from the TR03 study indicated that with close follow-up and guidance during the titration period, subject drop-out due to early symptoms associated with opiate initiation can be decreased, although not eliminated. Given that the completer's analysis in TR03 demonstrated a response rate of 50% (again acknowledging the small size of the cohort), increasing the number of subjects completing the study is expected to result in a somewhat higher all-treated response rate in the active arm than was seen in TR03.

5.2 Calculations

Approximately 30 - 45 sites are expected to participate in the current study. In SAS PROC POWER, the LOGISTIC setting was used to approximate the power for a chi-square test comparing the 2 treatment groups with respect to response, without site in the model, and a CMH

test comparing the 2 treatment groups with respect to response, with site in the model. In a model without site, the sample size was n=234 (117 per treatment group). The model with sites included was originally considered with the following assumptions: 30 sites of varying sizes (6 sites with 1% of the total sample each, 6 with 2%, 6 with 3%, 6 with 4%, 3 with 5%, 1 with 6%, 1 with 8% and 1 with 11%); and varying responder rates among sites (one fixed as having the lowest, and the next lowest having an odds ratio of 1.05 compared to the lowest and so on, until the one with the highest, which has an odds ratio of $[1.05]^{29} \approx 4.12$ compared to the lowest; this variation among sites is perhaps larger variation among sites than one would expect). In the PROC POWER runs, this site effect was specified in fixed order, and the site size was randomly scrambled. In 10 runs, the sample size needed for 90% power ranged from 239 to 242, averaging 240.7. Hence, the final target sample size is taken to be 240. With a sample size of 240, the study will have 80% power to detect a difference if the NAL ER 162 mg responder rate is as low as 41.8%.

To address the concern of the reliability of the estimates of treatment effectiveness from the previous studies, an adaptive mid-course sample size re-estimation procedure will be performed when 50% of the subjects have either completed the Week 14 primary endpoint assessment or terminated from the study early. The data for the re-estimation of sample size will be unblinded to an independent statistician and the sample size may be increased up to the predefined maximum allowable sample size if the conditional power is within the promising zone; therefore, this re-estimation will not inflate the type I error.

Given that the interim analysis is to be performed at 50% of the initial sample size (120 subjects), the targeted power is 90%, and the maximum allowable sample size is set at 1.5 times the initial sample size (360 subjects), the conditional power cut-off value (CPmin) is 41%². If the CP is between 41% and 90%, the number of subjects per treatment arm will be increased, up to the maximum allowable sample size for this study (360), to recover the targeted power of 90%. Since sample size re-estimation occurs only when the interim conditional power falls in the pre-specified “promising” range, and the study will not stop for efficacy regardless of the conditional power, the overall alpha will be protected, and the final analysis will be carried out using conventional tests, without the need for weighing the stage 1 and 2 results or adjusting the alpha value ²

6. ANALYSIS POPULATIONS

6.1. Modified Intention-To-Treat population (mITT)

The mITT population will consist of all randomized subjects who have received at least a single dose of the investigational product. The mITT population will be used for all efficacy analyses. In the event of a discrepancy between the randomized treatment and the actual treatment received, subjects will be analysed according to the randomization treatment.

6.2. Safety population (Safety)

The safety population will consist of all randomized subjects who have received at least a single dose of the investigational product. The safety population will be used in all safety analyses. In the event of a discrepancy between the randomized treatment and the actual treatment received, subjects will be analyzed according to the treatment they actually received.

6.3. Per-Protocol population (PP)

The per-protocol (PP) population will include all subjects in the mITT population without any major protocol deviations that could have influenced the validity of the data for the primary efficacy variable.

The deviations can include, but are not limited to: e.g. inclusion criteria 1-6 and exclusion criteria 1-3, 16, 17, and 19-25 must have been satisfied.

- Key inclusion/exclusion criteria not satisfied.
- Use of prohibited concomitant medications.
- Inadequate investigational product compliance (<50% compliant), which will be determined before breaking the blind.

The subjects to be excluded from the PP population will be identified in a blinded fashion and documented in a memo prior to the database lock and unblinding.

7. STATISTICAL CONSIDERATIONS AND ANALYSIS

7.2. Derived Variables

7.2.1. Baseline

The baseline WI-NRS value is calculated as the arithmetic mean of the WI-NRS values (minimum of 5 required) taken for eligibility review by site at the time of randomization. The Trialogics original average of the WI-NRS will be used as the baseline for all analysis. For all other efficacy and safety variables, baseline is defined as the last non-missing evaluation (including repeated and unscheduled assessments) taken prior to or on the first dose of study medication.

7.2.2. Changes from Baseline

For WI-NRS, the change from baseline during the double-blind period is described in [Section 7.3.1](#). For quantitative measurements other than WI-NRS, change from baseline will be calculated as:

Change from baseline = Test Value at Visit X – Baseline Value

If either value is missing, then the change from baseline will also be missing.

7.2.3. Date of First Dose of Study Drug

The date of randomization will be utilized for the date of first study drug dose, and will be referred to as the start date of study drug.

For the analysis referring to the open-label period, the date of the first administration of the extension titration medication will be considered as the start of this period.

7.2.4. Date of Last Administration of Study Drug

The date of last administration of the study drug in the double-blind period is derived as the last date when a dose of study drug was administered and recorded on the eCRF page of “Exposure (EX)” in that period.

The date of last administration of the study drug in the open-label period is derived as the last date when a dose of study drug was administered and recorded on the eCRF page of “Exposure (EX)” in that period.

The date of the last administration of the study drug for the study is derived as the last date when a dose of the study drug was administered and recorded on the eCRF page of “Exposure (EX)” whenever that occurs.

7.2.5. Study Day

The study day (e.g. adverse event onset, laboratory abnormality occurrence, vital sign measurement, dose interruption, etc.) will be calculated using the start date of double-blind study drug (Study Day 1) as the origin. Subsequent study days will be calculated as (date of assessment) – (start date of study drug) + 1.

For visits (or events) that occur prior to study day 1, the study day is defined as (date of visit (or events) – date of study day 1). There is no study day 0. Therefore, the study day displayed on the listing will be negative.

7.2.6. Exposure and Compliance

Duration of exposure (days) = (Date of last administration of study drug - Date of first administration of study drug) +1.

Compliance (%) = Number of tablets subject actually took/ Number of tablets subject was expected to take multiplied by 100.

Duration and compliance will be calculated for the double-blind and open-label periods, separately.

Statistical Analysis Plan (SAP)

7.2.7. Visit Window Definitions

Windowing is applicable to efficacy and safety endpoints, except for WI-NRS and SOWS for reporting purposes.

	BL*	Week 2	Week 6	Week 10	Week 14 **	Week 16	Week 20	Week 24	Week 28	Week 32	Week 36	Week 44	Week 52	Week 54	Week 56
Scheduled Day	1	14	42	70	98	112	140	168	196	224	252	308	364	378	
ItchyQoL	Day 1		22 to 56	57 to 84	85 to (titration start day-1)		titration start day to 154	155 to 182	183 to 224		225 to 280	281 to 336	>=337		
PAS and IGA-PN	Day 1			29 to 84	85 to (titration start day-1)		titration start day to 154	155 to 182	183 to 210	211 to 238	239 to 280	281 to 336	>=337		
PBI-P	Day 1			29 to 84	85 to (titration start day-1)		titration start day to 168		169 to 210	211 to 238	239 to 280	281 to 336	>=337		
Sleep Scale	Day 1		22 to 56	57 to 84	85 to (titration start day-1)		titration start day to 154	155 to 182	183 to 224		225 to 280	281 to 336	>=337		
Vital Signs	Day 1	8 to 28	29 to 56	57 to 84	85 to (titration start day-1)	titration start day to 126	127 to 154	155 to 182	183 to 210	211 to 238	239 to 280	281 to 336	337 to 371	>=372	
Clinical lab	Day 1	8 to 28	29 to 70		71 to (titration start day-1)				106 to 252			253 to 336	337 to 371	>=372	
Urinalysis	Day 1								99 to 280				>=281		

* If a Day 1 value is missing, then the last screening value is used as the baseline value.

** In the Week 14 column, the end of the window applies to subjects who go on to enter the open-label period. For subjects who don't enter the open-label period, the end of the window is 14 days later than that displayed in the column.

Statistical Analysis Plan (SAP)

Note: ECG windowing will be established by ERT, who will perform ECG analyses.

If two or more observations fall into the same window, the observation closest to the scheduled day will be used in the analysis. If there is a tie, the later observation will be used.

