7.3. Efficacy Derived Variables

7.3.1. WI-NRS

The WI-NRS is a PRO instrument, designed to quantify the intensity of worst itching experienced during a 24-hour period. The scale is a set of boxes, one for each number, from 0 (no itching) to 10 (worst possible itching). The NRS is a widely used instrument recommended by the IFSI for quantifying itch intensity as well as a useful instrument for grouping subjects into categories of itch intensity described as mild, moderate, or severe³: The itch NRS has been investigated in subjects with chronic pruritus of a variety of origins, and a high reliability and concurrent validity was found^{3,4}.

In this study, during the double-blind period, subjects will be asked to record the WI-NRS value daily, at approximately the same time each day, usually in the late afternoon or early evening. All WI-NRS information will be entered into the e-diary. During the open-label period, only a single value will be collected for the WI-NRS at each study visit. This will be collected using the same electronic diary format via web portal.

The primary endpoint depends on the change from baseline to Week 14. The calculation of the Week 14 value is described below.

For the 2-, 6- and 10-week visits, the WI-NRS will be calculated as the arithmetic means of the WI-NRS values on Study Days 8 through 14 (Week 2), 36 through 42 (Week 6), and 64 through 70 (Week 10), respectively, regardless of when the Weeks 2, 6 and 10 visits actually occur.

The Week 14 WI-NRS is calculated as follows:

- Case 1: Subject's Week 14 visit is on or after Study Day 98 (target day)
 - Use all values in the period Study Day 92 through Study Day 98
 - If there are ≥ 5 values, calculate the arithmetic mean of them
 - If there are < 5 values, calculate an arithmetic mean based on all of them plus any available values in the range from Study Day 99 till titration begins that will bring the total to 5 values, but do not use any values collected after titration begins. If this range has more values than necessary to bring the total to 5 values, use values closest to Study Day 98. If there are still less than 5 values, continue to use any available values in the first 3

days before Day 92 that will bring the total to 5 values. If this range has more values than necessary to bring the total to 5 values, use values closest to Study Day 92

- Case 2: Subject's Week 14 visit is before Study Day 98

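### The SAP's Week 14 window shuts out the Week 14 visit itself when the first extension-titration dose falls on the visit date

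*SAP*

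**What the plan says.** SAP 7.2.7 sets the Week 14 window for ItchyQoL, PAS and IGA-PN, PBI-P, the sleep scale and vital signs as "85 to (titration start day-1"). The laboratory window opens on Day 71 and has the same end. The next window opens on the start day itself: "titration start day to 154" for ItchyQoL, PAS/IGA-PN and sleep (Week 20; PBI-P runs to Day 168), and "titration start day to 126" for vital signs (Week 16). The next laboratory window opens on Day 106.

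SAP 7.2.3 gives the start as a calendar date: "the date of the first administration of the extension titration medication will be considered as the start of this period". No clock time or pre-dose condition is attached.

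Within a window, SAP 7.2.7 says: "If two or more observations fall into the same window, the observation closest to the scheduled day will be used in the analysis". For subjects who do not enter the extension, a footnote says "the end of the window is 14 days later than that displayed in the column".

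WI-NRS is outside these windows and has its own Week 14 rule in SAP 7.3.1.

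**The concern.** A boundary set at the day before first dosing is safe only if no one takes the first card dose on the visit date. The protocol does not rule that out. At the Week 14 visit (Protocol 9.1.3.3) the double-blind supply is taken back and the card is dispensed, and the card's first day has an evening dose only (Protocol 10.1.1). A subject assessed in the morning who starts the card that evening has a complete, blinded Week 14 visit that the SAP assigns elsewhere.

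Other SAP rules draw the line differently. The baseline rule (7.2.1) keeps records taken on the first-dose date. The double-blind TEAE period (8.7.1) ends at the first extension dose, not the day before. The WI-NRS rule keeps Day 98, or an earlier visit day, in Week 14.

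What is at stake:

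- **PAS 5a.** A subject without a Week 14 measurement is a non-responder (SAP 7.3.4, 8.6.3). PAS 5a is in the tested sequence in Protocol 13.4.6.3, in the SAP multiplicity section and in SAP 9.
- **ItchyQoL and PROMIS.** The Week 14 MMRM contrast loses the subject's Week 14 value. These are steps 2 and 4 in the protocol; their rank in the SAP is contradictory (see the objection).
- **IGA-PN activity.** The same non-responder rule applies.
- **Open-label tables.** If Week 20 is missed, a double-blind value is reported as an open-label Week 20 value.

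Only extension entrants are exposed, since non-entrants have a later window end.

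**Working it through.** **1. Window assignment.** Inputs: windows from SAP 7.2.7; target visit Day 98 with a tolerance of ±2 days (Protocol Table-1), so visits on Days 96 to 100. Let T be the titration start day; Week 14 ends on T − 1.

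| Visit day | T | Week 14 ends | ItchyQoL, PAS/IGA-PN, PBI-P, sleep | Vital signs | Laboratory |
|---|---|---|---|---|---|
| 96 | 96 | 95 | Week 20 | Week 16 | none |
| 98 | 98 | 97 | Week 20 | Week 16 | none |
| 100 | 100 | 99 | Week 20 | Week 16 | none |
| 96, 98 or 100 | visit + 1 | visit day | Week 14 | Week 14 | Week 14 |

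Days 97 and 99 behave the same way. With T = 98, laboratory results on Days 98 to 105 have no window. A Day 98 record in the Week 20 window is |98 − 140| = 42 days from the scheduled day, so any on-schedule Week 20 record displaces it. No other visit is scheduled between Day 85 and T − 1 to fill Week 14.

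**2. Does the first card dose fall on the visit date?** The documents do not say; dosing detail is left to the Pharmacy Manual and the subject instructions.

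- *Fits the visit date:* bottles retrieved and card dispensed at Week 14; evening-only first card day. The latter is weak evidence, because Protocol 9.3 has every new titration step start in the evening.
- *Fits Day 99:* double-blind dosing runs to W14D7 (14 × 7 = Day 98). From a Day 99 start, Days 101, 105 and 112 are card Days 3, 7 and 14, as in the first titration; from Day 98 they would be 4, 8 and 15, on a 14-day card. SAP 7.3.1 looks for extra values "from Study Day 99 till titration begins", and the urinalysis window opens on Day 99.

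**3. Effect of losing a share f of entrants' Week 14 records.** The documents give no Week 14 rates or correlations for these endpoints and no power for them, so the figures below are illustrations starting from an assumed 90% power at two-sided 0.05 (z = 3.242).

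*Binary endpoint.* If all responders enter the extension and f is the same in both arms, each rate p becomes p(1 − f). With unpooled variance v(a, b) = a(1 − a) + b(1 − b), the arm size cancels:

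z(f)/z(0) = (1 − f) × √[v(p₀, p₁) / v(p₀(1 − f), p₁(1 − f))]

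Example with p₀ = 30%, p₁ = 45%, f = 25%: 0.75 × √(0.4575/0.3980) = 0.804; z = 3.242 × 0.804 = 2.607; power = Φ(2.607 − 1.96) = 74%.

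*MMRM endpoint.* With Week 10 observed, random loss and Week 10–Week 14 correlation r, the variance factor is (1 − r²)/(1 − f) + r². Example with r = 0.4, f = 25%: 0.84/0.75 + 0.16 = 1.28; z = 3.242/√1.28 = 2.866; power = Φ(0.906) = 82%.

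| f | Binary z ratio | Binary power | MMRM variance factor (r = 0.4 / 0.8) | MMRM power |
|---|---|---|---|---|
| 0 | 1 | 90% | 1 / 1 | 90% |
| 10% | 0.88–0.93 | 81–86% | 1.09 / 1.04 | 87–89% |
| 25% | 0.73–0.83 | 66–77% | 1.28 / 1.12 | 82–87% |
| 50% | 0.53–0.65 | 40–56% | 1.84 / 1.36 | 67–79% |
| 90% | 0.20–0.28 | 10–15% | 8.56 / 4.24 | 20–35% |

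Binary ranges cover placebo rates of 20–50% and true differences of 10–20 points. At f = 5% binary power is 86–88%.

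**The case against.** The strongest reply is that the trigger is undocumented. The calendar evidence for Day 99 is coherent, and on that reading f is near 0: only visits on Day 99 or 100 with a same-day dose are affected. That stands as a limit on size. It does not rescue the rule, because the supply text supports the other reading and the analysis should not turn on a date the documents leave open.

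The conflict with the WI-NRS rule can also be read the other way. "Use all values in the period Study Day 92 through Study Day 98" is compatible with Day 98 being the last day before titration, so it is weak evidence of inconsistency. The baseline and TEAE rules show the contrast better, although the baseline rule concerns Day 1, where a same-day evening dose is expressly planned.

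The confirmatory exposure is narrower than a list of affected endpoints suggests. SAP 9 says ItchyQoL and PROMIS were removed from the ranking, while the SAP multiplicity section still lists them seventh and eighth. That section lists IGA-PN activity second, but SAP 8.6.3 gives it a confidence interval with no p-value. PAS 5a is the endpoint whose place in the sequence is clear in both documents.

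Finally, the power figures rest entirely on assumptions. That is so, and they should be read only as a scale.

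**Conclusion.** The concern holds. The window mechanism is certain from the SAP text: for any permitted visit day, a first card dose on the visit date removes that visit from Week 14. The practical size is uncertain because f is unknown; it runs from no effect at f = 0 to a serious loss of power if same-date starts are common. With equal f in both arms, the effect on binary endpoints is dilution of the difference by (1 − f) and lost power, not false positives.

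The primary WI-NRS endpoint, the WI-NRS mean change, adverse events and ECGs are not affected, nor are subjects whose first card dose comes on a later date than the visit.

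One related defect does not depend on f: the footnote gives non-entrants a window end counted from a titration start day that they do not have, so it cannot be programmed as written.

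This should be fixed; confidence is high on the mechanism and medium on its importance.

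**What to change.** Before database lock, amend the SAP 7.2.7 table:

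- End Week 14 on the titration start day for assessments made at the Week 14 visit or before the first card dose: Day 85 to start day, pre-dose; laboratory Day 71 to start day, pre-dose.
- Open the Week 20 and Week 16 windows after the first card dose, so that a post-dose record on the start day still has a window. Leave the Week 28 laboratory window at Day 106.
- Where assessment times are not collected, use the Week 14 visit label.
- For non-entrants, replace the footnote's offset with a fixed last study day.

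The supply and calendar passages on the first card day must also be reconciled; no view is taken here on which is right.

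The cost is a few table edits. Week 14 records of entrants who first dose on a later date do not change, and patients are not affected. If lock has passed, count the same-date starts and report the affected endpoints under both window definitions.

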2. If a **medication washout** is required, WI-NRS collection should begin following completion of the washout.
3. **Vital signs** are to be obtained after the subject has been seated for at least 5 minutes.
4. **ECGs** are to be performed in triplicate (3 serial ECGs at least 1 minute apart) after the subject has been in the supine position for at least 5 minutes. ECGs are to be transmitted to be read centrally by a core ECG laboratory. The average of the QTcF values from the triplicate ECGs will be performed and presented in a report to be used as the final eligibility assessment for the subject.
5. **Laboratory Evaluations:** Hematology and serum chemistry, LFTs, specified endocrine tests (at screening and Week 14 only: TSH, with reflex free T4 if above Upper Limit Normal (ULN) or below Lower Limit Normal (LLN), free testosterone [the fraction not bound to SHBG or albumin] and SHBG for males), and serum pregnancy test if WOCBP (regardless of sexual status at screening and baseline); urine pregnancy test to be performed by the local laboratory and confirmed to be negative prior to dispensing investigational product. TSH values above the upper limit of normal (ULN) should be repeated at the next study visit (or approximately 1 month later; whichever occurs first). If TSH remains above ULN, a Free T4 will be performed on the existing laboratory sample.
6. **AEs** are to be continually assessed starting with the signing of the informed consent. Concomitant medications should be collected from 14 days prior to the signing of consent. During the screening visit, subjects must be instructed to record any **new AEs or concomitant medication use** on the **Subject Symptom Log and Subject Medication Log** and to bring the logs to every visit (including the telephone contacts). Site to retrieve and review these logs at each subsequent visit prior to re-dispensing them or issuing new logs to the subject. Events of special interest should trigger the collection of additional information using the **AESI worksheet** and documented under the **AESI section of the Adverse Event eCRF**. Event details and both **subject and investigator narratives** should be thoroughly documented in the AESI worksheet and completed under the AESI

Table-1.

Schedule of Assessments – Double-blind, Placebo-controlled Period

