9.6 Premature Discontinuation of Investigational Product Treatment

Subjects who complete investigational product treatment through the full study treatment course are considered to have completed treatment with the investigational product (even if some doses have been missed). Subjects who discontinue investigational product, prior to 52 weeks of treatment will be considered to have prematurely discontinued and will be asked to complete the following visits (unless consent is withdrawn):

- If the decision to discontinue treatment is made during an onsite study visit (scheduled or unscheduled), perform the procedures and assessments outlined in the Off-Treatment visit, regardless of where they are in the study visit schedule.
- If the decision to discontinue treatment is made while the subject is not at a study visit, schedulea visit as soon as logically possible, but no later than 2 weeks later, to perform the procedures and assessments described in the Off-Treatment visit. Upon notification that the subject has permanently stopped dosing, the site should immediately update the subject’s status on the Trialogics web portal, in order to launch the SOWS, and instruct the subject to begin entering their SOWS data daily via the e-diary for the next 14 days.
- Schedule the subject to return to the clinic 2 weeks after completion of the Off-Treatment visit and perform the procedures and assessments outlined in the Last Visit, regardless of where they are in the study visit schedule.

- Schedule the End of Study telephone call with the subject 4 weeks after completion of the Off- Treatment visit and perform the procedures and assessments outlined in the schedule of events for this visit, regardless of where they are in the study visit schedule.
- If discontinuation of investigational product occurs any time between Day 1 and the Week 14 visit, the subject will be asked to complete the Off-Treatment visit, the Last Visit, and the End of Study visit telephone call, and to return to the clinic for the study schedule planned Week 14 visit.

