13.4.7 Safety Analyses

All on-treatment safety data will be assessed descriptively for AEs, SAEs, clinical laboratory measurements, vital signs, physical examinations and SOWS. ECG data will be analyzed in a separate report by ERT Clinical. The totality of these data addresses the secondary objective of characterizing the overall safety and tolerability of NAL ER in subjects with PN. Key parameters within the overall descriptive assessment of safety and tolerability are considered to be the rate of subjects having an SAE (Safety) and the rate of subjects discontinuing due to AEs (Tolerability).

No formal statistical analysis will be performed on safety outcomes; inferences, if any, will be derived through clinical review and interpretation.

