8.7.2 Clinical laboratory evaluations

All laboratory data will be summarized in the International System of Units (SI) and conventional units, respectively. Quantitative laboratory measurements reported as “< X”, i.e. below the lower limit of quantification (BLQ), or “> X”, i.e. above the upper limit of quantification (ULQ), will be converted to X for the purpose of quantitative summaries, but will be presented as recorded, i.e. as “< X” or “> X” in the listings. All laboratory assessments will be listed.

Descriptive statistics of absolute value and change from baseline (mean, SD, median, minimum, and maximum) for continuous assessments will be presented by windowed visits.

Laboratory Reference Ranges High/Low Criteria and Investigator's Assessment

Quantitative laboratory measurements will be compared with the relevant laboratory reference ranges in SI units and categorized as:

- Low: Below the lower limit of the laboratory reference range;
- Normal: Within the laboratory reference range (upper and lower limit included);
- High: Above the upper limit of the laboratory reference range.

Shift tables (Low, Normal, High) from baseline to worst post-baseline in lab parameters for each treatment group in the double-blind treatment period will be displayed.

Values outside the normal range will be flagged in the listings of individual subject data. Unscheduled visits will not be included in the analysis but will be listed.

Hepatobiliary Laboratory Abnormalities

Treatment emergent hepatobiliary laboratory abnormalities defined as values outside pre-specified thresholds will be summarized and listed by treatment and windowed visit. Treatment emergent is defined as any disorder/event recorded on the eCRF which started on or after the start date of treatment.

A summary of any treatment emergent hepatobiliary laboratory abnormalities according to different pre-specified thresholds will be made by treatment group:

- ALT or/and AST >3 x ULN and ≤ 5 x ULN;
- ALT or/and AST >5 x ULN;
- Total bilirubin >2 x ULN;
- (ALT and/or AST >3 x ULN) and Bilirubin > 2 x ULN;

- Hy's law laboratory criteria: (ALT and/or AST $>3 \times$ ULN) and Bilirubin $> 2 \times$ ULN and ALP $<2 \times$ ULN.

ULN = Upper limit of normal range.

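### SAP 7.2.7 places laboratory and vital-sign values in visit weeks without using the last-dose date, so early stoppers' off-drug values enter the treatment-week summaries

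*SAP*

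**What the plan says.** SAP 7.2.7 sets its scope: "Windowing is applicable to efficacy and safety endpoints, except for WI-NRS and SOWS for reporting purposes". Laboratory tests and vital signs are therefore windowed. Days are counted from the start of double-blind drug: "Subsequent study days will be calculated as (date of assessment) – (start date of study drug) + 1" (SAP 7.2.5).

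- Laboratory windows in the double-blind period are Days 8 to 28 (Week 2), 29 to 70 (Week 6), and Day 71 to the day before extension titration (Week 14).
- Vital-sign windows are Days 8 to 28, 29 to 56 and 57 to 84 (Week 10), then Day 85 onward (Week 14).
- For subjects who do not enter the extension, the Week 14 window ends 14 days later.
- Within a window: "If two or more observations fall into the same window, the observation closest to the scheduled day will be used in the analysis". Ties go to the later value.

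SAP 7.2.4 derives the date of last dose, but 7.2.7 does not use it. SAP 8.7.2 says that descriptive statistics "for continuous assessments will be presented by windowed visits", and 8.7.3 does the same for vital signs. Neither section, nor 8.7, sets an on-treatment limit.

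Protocol 13.4.7 states: "All on-treatment safety data will be assessed descriptively for AEs, SAEs, clinical laboratory measurements, vital signs, physical examinations and SOWS". The synopsis has the same on-treatment basis.

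Under Protocol 9.6, a subject who stops before Week 14 is asked to complete the Off-Treatment visit, the Last Visit two weeks later and a telephone call, "and to return to the clinic for the study schedule planned Week 14 visit". All three clinic visits include laboratory tests and vital signs (Protocol 9.1.3.3 and 9.1.3.6). In the double-blind schedule, Table-1 footnote 5 lists "specified endocrine tests (at screening and Week 14 only".

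**The concern.** The protocol schedules safety measurements after drug has stopped, and the SAP has no rule to keep them apart from measurements made on drug. A Week 6 or Week 14 mean change can then mix subjects on 162 mg BID with subjects who stopped weeks before, in one unmarked row. The SAP does have a row for completers' off-drug values (Week 54), but it too is set by study day (Day 372 or later).

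By-visit means, and the hepatobiliary abnormality counts that 8.7.2 presents by windowed visit, would describe neither drug exposure nor recovery. The endocrine tests are the most exposed. Protocol 7.2.3 names endocrine effects as one of two organ systems under further evaluation. For a subject on schedule, Week 14 is their only post-baseline time point with a placebo comparison.

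**Working it through.** The plan states no figure on this point, so there is none to reproduce. The check applies the SAP rule to each possible stop day and then gives a range for the share of affected values.

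**Step 1: which value is chosen.** Stop days 1 to 97 were enumerated. Each subject has the scheduled visits up to the stop, an Off-Treatment visit, a Last Visit 14 days after that, and the Day 98 visit. Protocol 9.6 allows the Off-Treatment visit up to 2 weeks late, so delays of 0 and 14 days were run. Assumption: the SAP gives no base day for the Week 14 window of a subject with no extension titration, so Day 98 + 14 = Day 112 was used. The table shows stop days for which the chosen value is at least 14 days off drug.

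| Row | No delay | On-drug value displaced (no delay) | 14-day delay |
|---|---|---|---|
| Week 2, both | 1 to 7 | none | 1 to 13 |
| Week 6, both | 15 to 35 | 29 to 35 | 1 to 41 |
| Week 10, vital signs | 43 to 63 | 57 to 63 | 29 to 69 |
| Week 14, both | 1 to 84 | laboratory 71 to 84; vital signs none | 1 to 84 |

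At Week 14 the chosen value is 98 − 84 = 14 to 98 − 1 = 97 days off drug. With the delayed visit, Week 6 and Week 10 values are 14 to 28 days off drug and no on-drug value is displaced.

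Examples:

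- Stop on Day 28, Last Visit on Day 42: Day 42 is the only Week 6 value, 14 days off drug. Nothing is displaced; the window alone admits it.
- Stop on Day 75: laboratory values on Days 75, 89 and 98 share the Week 14 window. Distances to Day 98 are 23, 9 and 0, so the Day 98 value (23 days off drug) is used and the Day 75 value is not.
- Extension stop on Day 182: the Last Visit on Day 196 is 0 days from the Week 28 target and the Day 182 laboratory value is 14 days from it, so Day 196 is used.

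A double-blind stopper's Last Visit cannot reach the Week 54 row. In the extension, with no delay, the same is true of any stop up to Day 357, since 357 + 14 = 371.

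SAP 8.7.2 leaves unscheduled visits out of the analysis, but these visits are scheduled, so that does not remove them. SAP III.A asks stoppers to attend all remaining visits to Week 14, which conflicts with SAP Table 1 footnote 10 and would add more off-drug values.

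**Step 2: are these values off drug?** Half-life is 6.6 to 9.6 h (Protocol 7.2.2). Fourteen days is 336 h: 336/9.6 = 35 and 336/6.6 = 51 half-lives.

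**Step 3: share of Week 14 values off drug.** TR03 (Protocol 13.1): 12 of 18 NAL ER 162 mg and 20 of 22 placebo subjects completed, so non-completion d is 6/18 = 33.3% and 2/22 = 9.1%. With r the share of stoppers who return for Week 14:

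share = d·r / ((1 − d) + d·r)

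| r (assumed) | NAL ER | Placebo |
|---|---|---|
| 100% | 33% | 9% |
| 50% | 0.167/0.833 = 20% | 5% |
| 25% | 0.083/0.750 = 11% | 2% |

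With NAL ER non-completion anywhere from 10% to 40% and the same return rates, the share runs from 3% to 40%.

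**The case against.** The word on-treatment comes from the protocol. The SAP labels its rows by visit week only, so a reader who infers that off-drug values are reported as on-treatment results goes further than the text. The protocol sentence also lists SOWS, which is collected only after drug stops, so its use of on-treatment cannot be strict. SAP 8.7.1 likewise assigns adverse events by period with no last-dose limit. This stands: the defect is a missing definition and restriction, not a false label.

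A reader might also infer that NAL ER safety signals are diluted generally. The documents do not support that. The laboratory shift tables use the worst post-baseline value, and an added off-drug value cannot hide an on-drug extreme. Adverse event, SAE and discontinuation tables are untouched, ECG is windowed separately, and every laboratory value is listed. The two key safety parameters in Protocol 13.4.7 (SAE rate and discontinuation due to adverse events) are unaffected, and safety is descriptive.

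On endocrine tests, the panel in Table-2 footnote 5 includes TSH and free testosterone. An early stopper can therefore have a value at the Off-Treatment visit, which remains eligible for the shift table. Protocol 7.2.3 also says that no data suggest specific endocrine relevance for NAL ER. Both points lower the stakes. They do not change what enters the Week 14 row.

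Protocol 13.1 expects fewer early drop-outs than in TR03, and subjects who withdraw consent need not return. Plasma clearance does not show that TSH, testosterone or liver values revert.

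**Conclusion.** The concern holds for by-visit laboratory and vital-sign summaries. Following SAP 7.2.7 as written puts scheduled off-drug values into treatment-week rows, and for some stop days it passes over an on-drug value in favour of an off-drug one. That sits badly with the protocol's on-treatment basis. SAP section 9 does not list it as a change from the protocol.

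The size is unknown. The shares of 11% to 33% (NAL ER) and 2% to 9% (placebo) rest on TR03 non-completion and assumed return rates; the documents give neither figure for TR11. If an effect reversed fully off drug, the mean change would shrink to (1 − share) of its on-drug value: 0.89 at 11% and 0.67 at 33%. A reader might take 0.67 as the expected loss. It is the extreme of this range, because it needs TR03 drop-out, full return and full reversal together.

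Greater dilution on NAL ER than on placebo is a reasonable inference for double-blind by-visit rows, since placebo has no drug effect to lose and TR03 non-completion was higher on NAL ER. It is not a documented fact for TR11. It has no meaning in the extension, where all subjects receive NAL ER.

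**What to change.** In SAP 7.2.7, define an on-treatment cut-off after the last dose for laboratory and vital-sign data. About 2 days is one option (5 × 9.6 h = 48 h); the sponsor may justify another. Then:

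- admit only assessments within the cut-off to the treatment-week by-visit rows;
- show later values, whatever their study day, in separate rows: Off-Treatment visit if late, Last Visit, and Week 14 off drug;
- leave the worst-post-baseline shift tables on all post-baseline values, so that late-emerging abnormalities stay visible.

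The cost is SAP wording and one flag from the last-dose date that SAP 7.2.4 already derives. The downside is smaller numbers in the treatment-week rows. Because an Off-Treatment visit may be up to 2 weeks late, a short cut-off will move some values close to the last dose into the separate row, where they remain reported.
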